16.2. Statistical Analysis

A comprehensive analysis of the study results will be performed at the end of stage 1 and an interim Clinical Study Report will be released. An analogous analysis will be performed at the end of stage 2 with data from stage 1 + stage 2 and a final Clinical Study Report will be released.

The final Statistical Analysis Plan (SAP) will be submitted and approved by the DSMB prior to the database lock for the final study analysis (stage 1 + stage 2).

16.2.1. Analysis Sets

Five analysis sets will be used in this study:

- *All enrolled subjects:* composed of all subjects who signed an informed consent form and were enrolled in the study.
- Safety Analysis Set (SAF): composed of all enrolled subjects who received at least one dose of a study drug. This set will be used for safety analyses.
- *Full Analysis Set (FAS):* composed of all enrolled subjects with no current injection drug use at screening who received at least one dose of a study drug. This set will be used for the primary analysis of SVR endpoints.
- Per Protocol Set (PPS): composed of all subjects in the FAS who did not prematurely discontinue the study, had an adherence to SOF+RDV ≥ 90%, had no missing SVR12 results and had no major protocol deviation during the study. The PPS will only be used for the secondary analysis of SVR endpoints.
- *Pharmacokinetic Analysis Set (PKAS):* composed of all enrolled subjects who participated in the intensive PK analysis or for whom sparse PK data are available.

The reasons for excluding a subject from any of the analysis sets will be described in the clinical study report.

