13.5. Follow-up visits

13.5.1. SVR4, SVR 12, SVR 24 and end of study visit

The week 4 post-treatment visit will have a window of -1 day and +7 days

The week 12 post-treatment visit (SVR 12, key endpoint) will have a window of -1 day and +28 days.

The week 24 post-treatment visit (SVR 24) will have a window of -3 days and +28 days.

This final visit will focus on assessing SVR 24 weeks after treatment discontinuation. Post-treatment study follow-up is of critical importance and is essential to preserving subject safety and the integrity of the study. Subjects who discontinue study treatment must continue to be followed for collection of outcome and/or survival follow-up data.

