13.5.2. Long term follow-up visits

A series of long-term follow-up visits will be implemented retrospectively for stage 1 (only for newly consented patients with virological failure) and for stage 2.

A representative subset of the cured patients (i.e achieving SVR12) will be followed up for one year after end of treatment to assess durability of response. One additional follow-up visit will be scheduled 12 months (+/- 28 days) after the end of treatment visit

All patients with virological failure at SVR12 or SVR24 will be followed up for three years after end of treatment or until they receive another treatment for HCV, whichever comes first. Five additional follow-up visits will be scheduled at one year, 18 months, 2 years, 30 months and 3 years after the end of treatment visit. Each of these long term follow-up visits has a window of +/- 28 days.

The following assessments will be performed at each long term follow-up visit, depending on cirrhosis status and achievement of SVR12 and SVR24:

	Non-Cirrhotics	Cirrhotics
Cured patients	HCV viral load and genotyping	HCV viral load and genotyping
-	Biochemistry and Haematology blood	Biochemistry and Haematology blood
(1 year FU post	sample ¹	sample ¹
end of treatment)	Symptom directed assessment	Symptom directed assessment
ŕ	AE review ²	AE review ²
Stage 2 only		INR ³
		Fibroscan ⁴
		Ultrasound⁵
Patients with virological failures (3 years FU post end of treatment)	HCV viral load and genotyping and resistance assessment Biochemistry and Haematology blood sample ¹	HCV viral load and genotyping and resistance assessment Biochemistry and Haematology blood sample ¹
Stage 1 and stage 2	Symptom directed assessment AE review ² INR ³ Fibroscan ⁴	Symptom directed assessment AE review ² INR ³ Fibroscan ⁴ Ultrasound ⁵

¹ Biochemistry and haematology including ALT and AST and bilirubine (direct and free)

²AE monitoring as per safety section

³ INR is performed to assess the evolution of the liver condition

⁴A Fibroscan is performed to assess the evolution of fibrosis

⁵ An ultrasound is performed to assess the occurrence of HCC as part as the standard of care.

14. Samples management

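### In the secondary per-protocol analysis, the study-discontinuation clause has no time limit, so it can remove subjects who already have a valid SVR12 result

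*Protocol*

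**What the plan says.** Protocol section 16.2.1 builds the PPS from four conditions. It is "composed of all subjects in the FAS who did not prematurely discontinue the study"; adherence must be at least 90%; and subjects must have "had no missing SVR12 results and had no major protocol deviation during the study". The discontinuation condition carries no date. The role of the set is limited: "The PPS will only be used for the secondary analysis of SVR endpoints". Of the FAS, which has no completion condition, the same section says: "This set will be used for the primary analysis of SVR endpoints".

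On timing, section 13.5.1 states: "The week 12 post-treatment visit (SVR 12, key endpoint) will have a window of -1 day and +28 days". The main study then runs on to the week 24 post-treatment visit, of which it says: "This final visit will focus on assessing SVR 24 weeks after treatment discontinuation". Section 13.5.2 makes later follow-up depend on outcome. A subset of cured subjects is seen at one year, while virological failures "will be followed up for three years after end of treatment or until they receive another treatment for HCV, whichever comes first".

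**The concern.** A per-protocol set for a week 12 endpoint should be fixed by what happened up to that endpoint. Here one entry condition can be failed after the SVR12 sample has been taken. An event at, say, week 18 cannot alter a week 12 viral load, yet it removes that viral load from the per-protocol SVR12 rate.

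Leaving may also be related to the result. Treatment is open label (section 9.2.1), viral load is run for all subjects at the SVR12 visit (synopsis), and follow-up beyond week 24 is assigned by outcome. Sites will therefore know the result, and subjects probably will too. If failures leave more often than cured subjects, the per-protocol SVR12 rate is too high; if cured subjects leave more often, it is too low. If leaving is unrelated to outcome there is no bias, but valid results are still lost. Few failures are expected, so a handful either way is a noticeable share of them.

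**Working it through.** The protocol gives no figure on this point, so the check has two parts: what the clause acts on, and how far it could move the rate.

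**What the clause acts on**

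1. Study discontinuation is not treatment discontinuation. Section 3.2.2 lists them as separate endpoints, and sections 6.1 and 9.7 keep subjects who stop treatment in the study.
2. A subject who leaves before week 12 has no SVR12 result. Section 11 lets SVR24 stand in for a missing SVR12, but someone who has left has no SVR24 either, and it bars SVR4 as a substitute. The missing-result condition already removes this subject.
3. What remains for the discontinuation clause is mainly departure after SVR12. Counting from end of treatment, the SVR12 window is day 84 − 1 = 83 to 84 + 28 = 112. The week 24 window is day 168 − 3 = 165 to 168 + 28 = 196. The gap is between 165 − 112 = 53 and 196 − 83 = 113 days.
4. Departure in that gap is possible. Section 6 allows withdrawal at any time, and section 6.4 allows loss to follow-up after three failed contact attempts over 2 months.

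**How far it could move the rate**

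Let S and F be the cured and failed subjects who meet every other PPS condition, and a and b the numbers of each who leave after SVR12. The per-protocol rate becomes (S − a) / (S − a + F − b).

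Assumed: S = 570, F = 20. The undisturbed rate is 570/590 = 96.6%.

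| Assumed departures | Rate | Shift (points) | Results lost |
|---|---|---|---|
| 6 cured, 7 failures | 564/577 = 97.7% | +1.1 | 13 |
| 57 cured, 0 failures | 513/533 = 96.2% | −0.4 | 57 |
| 57 cured, 2 failures (10% of each) | 513/531 = 96.6% | 0 | 59 |

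The same calculation can be run in proportions. With true rate p and departure shares d_s (cured) and d_f (failures), the rate is p(1 − d_s) / [p(1 − d_s) + (1 − p)(1 − d_f)]. For N = 600, p = 95%, d_s = 2% and d_f = 10%, this gives 558.6 / (558.6 + 27.0) = 95.4%, a shift of +0.4. Other assumed pairs:

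| d_s / d_f | Shift at p = 95% | Shift at p = 90% |
|---|---|---|
| 5% / 5% | 0 | 0 |
| 2% / 10% | +0.4 | +0.7 |
| 5% / 20% | +0.8 | +1.4 |
| 2% / 50% | +2.4 | +4.6 |
| 10% / 0% | −0.5 | −1.0 |

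Once post-SVR12 departure no longer counts, the shift is zero in every row and no valid result is lost.

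**The case against.** The case for leaving the text alone has several parts, and much of it stands.

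- **Only a supportive analysis is touched.** This stands. A subject who leaves after SVR12 keeps the observed result in the FAS, and the 85% goal in section 16.1.1 concerns the overall SVR12 rate.
- **Failures need not leave to be retreated.** This stands. Section 9.4 bars other anti-HCV medication only until 12 weeks post-treatment. The words "or until they receive another treatment for HCV, whichever comes first" in section 13.5.2 mark a planned end of long-term follow-up, so they are no evidence of early departure. The offer of three years of follow-up is itself a reason to stay.
- **A missed week 24 visit is not by itself discontinuation.** This stands. Under section 6.4, a reachable subject who attended week 12 and skipped week 24 is not lost to follow-up.
- **The illustration is extreme.** This stands. Losing 7/20 = 35% of failures against 6/570 = 1.05% of cured subjects is a roughly 33-fold difference that nothing in the protocol supports. Even then the rate stays far above 85%.
- **One set serves SVR4, SVR12 and SVR24, and completion matters for SVR24.** This is true for SVR24, where section 11 forbids filling in from earlier visits. It does not justify the clause for the earlier endpoints.
- **Exclusions will be reported, and the statistical analysis plan may narrow the clause.** Reporting shows the loss but does not restore the results. The protocol fixes the definition itself, so this is not a detail left open for the analysis plan.

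A reader might infer that subjects decide whether to stay after seeing their result, and that the per-protocol rate is therefore inflated. The documents do not support this. Nothing says subjects are told the SVR12 result before that decision, and the direction of any difference in departure is unknown.

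**Conclusion.** The point holds for the secondary per-protocol analysis only. As written, the clause conditions a week 12 endpoint on later behaviour and, for SVR12, adds almost nothing to the missing-result condition except the loss of valid results. Bias is possible, not certain. In the main illustration it runs from about −0.4 to +1.1 points, and it is zero if leaving is unrelated to outcome. Larger shifts need stronger assumptions, such as half of all failures leaving. All departure rates and true rates here are assumptions. The point does not depend on whether the long-term phase counts as part of the study, which the protocol does not settle; the week 12 to 24 gap is enough. It would be wrong to conclude that the primary SVR12 result is at risk. Severity is minor to moderate.

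**What to change.** In section 16.2.1, and in the statistical analysis plan to match, make both the discontinuation and the missing-result criteria specific to the endpoint:

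- **SVR12:** exclude only subjects who discontinued the study before the SVR12 assessment, or delete the clause, since a non-missing SVR12 already covers it.
- **SVR4:** require only an available SVR4 outcome and no discontinuation before that assessment. Requiring an SVR12 result here would again condition on a later event.
- **SVR24:** apply the clause up to the week 24 visit.

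The cost is a few lines of text, with no new data and no change to study procedures. The downside is that per-protocol denominators will differ slightly between endpoints, which the planned description of exclusions can show.

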16.2.2. Subject Flow Diagram

A subject flow diagram will describe eligibility, enrolment, receipt of intended treatment, completion of study visits, and retention in the study and availability of primary endpoint (www.consort-statement.org).

16.2.3. Descriptive Statistics

Participant's characteristics at base line and over time will be tabulated. Categorical variables will be described using frequencies and proportions, and discrete and continuous variables using means (standard deviations), medians (25th; 75th percentiles) and ranges (minimum-maximum).

Most important subjects' characteristics at enrolment include liver disease classification (F0 to F4), HCV viral load (median, IQR), haemoglobin level, anthropometry and demographic characteristics.

16.2.4. Efficacy Analysis

The efficacy of SOF-RDV will be evaluated overall and for each of the pre-specified subgroups: presence/absence of cirrhosis, genotype, prior/no prior therapy, and HIV/no HIV co-infection.

Non-virological failures (including deaths and lost to follow-ups), on-treatment virological failures and virological relapses, will be considered as failures. Reinfections are not considered as failures.

Time-to-event endpoints will be estimated using the Kaplan-Meier method. Changes in continuous variables from baseline will be assessed using Wilcoxon signed-rank test.

In exploratory analyses, multivariable logistic regression models and Cox proportional hazards regression models may be used to evaluate risk factors associated with binary and time-to-event endpoints, respectively.

16.2.5. Safety Analysis

Adverse events will be described during the study period, until 24 weeks after treatment discontinuation. AEs and Medical History will be coded using MedDRA and tabulated by severity / DAIDS AE grading table version 2/ November 2014. Causality of AEs for each sudy drug will also be tabulated.

The number and percentage of subjects who experienced each of the safety events listed as secondary endpoints will be presented overall, by assigned treatment duration and by key subgroup. In addition, the number and percentage of subjects who experienced these events will be

summarized by MedDRA System Organ Class (SOC) and Preferred Term (PT) and presented overall and by assigned treatment duration.

Safety and tolerance of the study agents will be evaluated by summarizing the number and percentage of subjects with documented Grade 3 or higher adverse events; each summary will be conducted overall and by assigned treatment duration. The proportion of subjects experiencing Grade 3+ adverse events will be presented overall and by assigned treatment duration , with these proportions bounded by exact 95% confidence intervals; this will also be done for the proportions of subjects with Grade 3+ intensity adverse events which have been judged to be at least possibly related (possibly/probably/definitely related) to treatment.

Serious Adverse Events will be described by individual narratives based on the SAE reports provided by the site investigators.

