4.2. Schematic diagram of study design

4.3. Study duration and duration of subject participation

Study duration for the subject:

12/24 weeks on-treatment for non-cirrhotic/cirrhotic patient

+ 24 weeks post-treatment follow-up

Total = 36/48 weeks for non-cirrhotic/cirrhotic patient

+ additional long term follow-up of 6 months for subset of cured patients: total of about 16/19 months for such non-cirrhotic/cirrhotic patients

or

+ additional long term follow-up of 30 months for all patients with virological failure: total of about 40/43 months for such non-cirrhotic/cirrhotic patients

Study duration stage 1:

Actual first enrollment: October 2016 in Malaysia, April 2017 in Thailand Actual last visit completed (Follow-up visit Week 24): April 2018 Study duration stage 2: Actual first enrollment: January 2019 in Malaysia, August 2019 in Thailan

Actual first enrollment: January 2019 in Malaysia, August 2019 in Thailand Estimated last visit completed (end of long term follow-up): up to Q4 2023

5. Selection of subjects

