14.5. Laboratory analysis

All laboratory analysis will be performed in accordance to the laboratory manual derived from the individual institution.

15. Assessment of safety

- Incidence of premature discontinuation of treatment and premature discontinuation of study – for any reason, for non-compliance, and for safety-related reasons
- Incidence of adverse events, and laboratory abnormalities during the observation period, i.e. from signature of informed consent to 24 weeks after end of treatment;
- Incidence of serious adverse events from signature of informed consent to 24 weeks after end of treatment;
- Incidence of grade 3-4 clinical and laboratory Aes through 24 weeks after the end of treatment.

Subjects will be monitored for clinical and biological adverse events. These will be reported using DAIDS toxicity grading tables xi.

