15.2. Adverse events reporting

15.2.1. Detecting and documenting AE

The investigator is required to report all directly observed Aes and all Aes reported by the trial subject using concise medical terminology. In addition, at each visit the subjects will be questioned about the occurrence of Aes, with a generic question such as "Since your last visit have you experienced any health problems?"

Stage 1 (for patients who did not consent for long-term follow-up visits): The AE reporting period for this stage of the trial begins upon subject enrolment in the trial (after signature of informed consent for treatment initiation) until 24 weeks' post-treatment completion.

Stage 1 (for patients who consented for long-term follow-up visits) and stage 2: The AE reporting period for this stage of the trial begins upon subject enrolment in the trial (after signature of informed consent for treatment initiation) until:

- End of long-term follow-up visits (SVR 24 + one additional visit for cured patients and 5 additional visits for virological failures): for all serious adverse events.
- End of long-term follow-up visits (SVR 24 + one additional visit for cured patients and 5 additional visits for virological failures): for all liver-related serious and non-serious adverse events.
- 24 weeks' post-treatment completion (SVR 24 visit): for adverse events not associated with any liver-related and not serious.

For both stages of the study:

Serious adverse events will be followed and reported until resolution or stable state.

Information on Aes must be evaluated by a physician. Each adverse event is to be classified by the investigator as serious or non-serious. This classification will determine the reporting procedure for

the event to DNDi and Regulatory Authorities/Ethics Committees (as per local regulatory requirements).

All patients who have Aes, whether considered associated with the use of the investigational product or not, must be monitored to determine the outcome. The clinical course of the AE will be followedup according to accepted standards of medical practice (i.e. until they are resolved or the investigator assesses them as chronic or stable or the subject participation in the trial ends (i.e., until a final report is completed for that subject), even after the end of the period of observation, until a satisfactory explanation is found or the Investigator considers it medically justifiable to terminate follow-up.

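### Serious and liver-related adverse events are collected to the end of long-term follow-up, but the planned description stops at 24 weeks, so late events have no planned count

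*Protocol*

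**What the plan says.** **Description and incidence.** Section 16.2.5 (Safety Analysis) reads: "Adverse events will be described during the study period, until 24 weeks after treatment discontinuation". The synopsis repeats the sentence, and neither place exempts any event type. The list that opens section 15 (Assessment of safety) includes "Incidence of serious adverse events from signature of informed consent to 24 weeks after end of treatment", and sets the same limit for AEs in general and for grade 3-4 events.

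**Collection.** Section 15.2.1 sets three windows for Stage 2 and for Stage 1 subjects who consented to long-term visits:
- SAEs run to the end of long-term follow-up ("and 5 additional visits for virological failures): for all serious adverse events").
- Liver-related events run equally long, and this covers "serious and non-serious adverse events".
- The 24-week stop is kept only "for adverse events not associated with any liver-related and not serious".

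**Who is followed.** Under section 13.5.2, virological failures "will be followed up for three years after end of treatment or until they receive another treatment for HCV, whichever comes first"; from Stage 1 these are "only for newly consented patients with virological failure". A subset of cured Stage 2 subjects is seen once more, one year after treatment. AE review is scheduled for both groups, with and without cirrhosis, and a footnote refers to the safety section for how it is done.

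**Other safety outputs.** Section 16.2.5 counts the safety events listed as secondary endpoints. In section 3.2.2 the SAE item is treatment-emergent SAEs, while death is listed without that label. Section 16.2.5 also promises individual SAE narratives and gives no time limit for them.

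**The concern.** The protocol keeps two event classes open past week 24 on purpose, then closes their description at week 24 in three places. It is not simply silent. An analyst who follows sections 15 and 16.2.5 literally would leave out events that section 15.2.1 requires sites to report.

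At stake is the late liver-safety record. Section 13.5.2 schedules INR, Fibroscan and, in cirrhotic subjects, ultrasound for liver cancer during this period. The schedule for cirrhotic patients (section 7.2) requires suspected or confirmed liver cancer to be reported as an AE. Without a count and a denominator, a reader of the final report could not tell how many followed subjects had a late SAE or liver event, or how long they were observed.

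**Working it through.** **1. Windows side by side** (Stage 2, and Stage 1 subjects who consented to long-term follow-up)

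| Event class | Collected until (15.2.1) | Described until (15, 16.2.5, synopsis) | Planned output after week 24 |
|---|---|---|---|
| Neither serious nor liver-related | Week 24 post-treatment | Week 24 | None needed |
| SAE | End of long-term follow-up | Week 24 | Narratives only |
| Liver-related, non-serious | End of long-term follow-up | Week 24 | None |

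For Stage 1 subjects without long-term consent, collection also ends at week 24, so there is no mismatch.

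**2. Does another clause close the gap?**
- The counts in section 16.2.5 cover the secondary safety endpoints, which for SAEs are treatment-emergent ones. Section 15 stops SAE incidence at week 24.
- Narratives describe cases. They give neither a count nor a number at risk.
- The footnote in section 13.5.2 points back to the safety section and adds no output.
- The Thai regulatory tabulation in section 21.2 covers suspected serious reactions only and is not a trial analysis.

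None of these plans a count of late SAEs or any output for late non-serious liver-related events.

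**3. Length of the uncovered period**

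Inputs: follow-up of 36 months (failures) or 12 months (cured subset) after treatment, from section 13.5.2; week 24 as the cut-off; 365.25/12 = 30.44 days per month.

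- 24 weeks = 168/30.44 = 5.52 months.
- Virological failures: 36 − 5.52 = 30.48 months, or 30.48/36 = 85% of their post-treatment time. Section 4.3 states 30 months.
- Cured subset: 12 − 5.52 = 6.48 months, or 6.48/12 = 54%. Section 4.3 gives this as "additional long term follow-up of 6 months for subset of cured patients".

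The protocol's own figures are reproduced to rounding. For failures the period is a maximum, because follow-up ends at retreatment.

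**4. How many subjects? A rough illustration only**

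Assume SVR12 between 95% and 87%, the range of Figure 3 in section 16.1.3.
- Stage 2: 300 × 0.05 = 15 to 300 × 0.13 = 39 SVR12 failures.
- Stage 1: between none and 39 more, depending on SVR12 and new consent.
- Together: 15 + 0 = 15 to 39 + 39 = 78, out of 600.

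Neither end is a bound. The range includes non-virological failures, who do not enter this follow-up. It omits relapses after SVR12 and the additional Stage 1 stratum of up to 150 people who inject drugs. The size of the cured subset is not stated, so no total can be given. The point does not depend on these numbers.

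**The case against.** The strongest reply is that collecting longer than one tabulates is not in itself an error. Week 24 is the last visit that all subjects share. After it, only groups selected partly by treatment outcome are followed, and for different lengths of time. A common 24-week window is therefore the right basis for incidence tables. This stands, and it limits the remedy. A reader might infer that the 24-week limit on SAE incidence should be lifted. The documents do not support that, since failures would then contribute far more observation time than cured subjects and would be over-represented.

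A second reply is that late-event listings are ordinary SAP content, and that section 16.2 foresees a final SAP, which is not at hand. This stands in part: one cannot say that the trial has no plan for these data, only that the protocol states none. But the protocol fixes a cut-off for every event type, so an SAP that added late events would go beyond sections 15 and 16.2.5 as worded.

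A third reply is that much of the important late information survives. This is also right. Narratives have no time limit, SAEs reach the sponsor within 24 hours, many liver cancer and decompensation events would qualify as serious, and late deaths may be counted because that endpoint carries no treatment-emergent label. It would be wrong to infer that late serious events go unreported. What is missing is their count and denominator, and any output for late liver-related events that are not serious.

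Finally, the long-term visits are justified mainly by durability of response and persistence of resistance, and no safety objective is tied to them. That lowers the weight of the point but does not explain why section 15.2.1 singles out these two event classes for longer collection.

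**Conclusion.** The point holds in a limited form. The 24-week cut-off is stated for all event types, while SAEs and liver-related AEs are collected to the end of long-term follow-up. As the protocol is written, late SAEs have narratives without a count or denominator, and late non-serious liver-related AEs have no output. The uncovered period is up to about 30 months for virological failures and about 6 months for the cured subset. How many events fall in it cannot be estimated from the protocol.

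A reader might go further and infer that the trial's efficacy or main safety conclusions are affected. They are not: SVR12 and the 24-week tables do not change. The conclusion rests on the protocol text alone and would be met in substance if the SAP already plans a late-event summary, though the protocol wording would still need aligning. The weight is minor to moderate, and the change is a cheap improvement.

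**What to change.** Leave the 24-week window as it is for all existing AE and SAE incidence tables. In section 15, section 16.2.5 and the synopsis, add a sentence to this effect:

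> SAEs and liver-related AEs occurring after post-treatment week 24 will be reported separately, in a descriptive listing or summary with subject counts, and will not be pooled with the 24-week tables. Results will be shown for the cured subset and for virological failures, with the number of subjects entering long-term follow-up and their follow-up time as denominator.

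If the final report precedes the last long-term visit, issue this part as an addendum.

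The cost is one sentence in three places and one listing or summary. No new visits, tests or data are needed. The drawback is that the late data are sparse, selected and uncontrolled, so the output can only be descriptive.
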